7.4 MRC CTU RESPONSIBILITIES

Medically-qualified staff at the MRC CTU and/or the Chief Investigator (or a medically-qualified delegate) will review all SAE reports received. The causality assessment given by the local investigator at the site cannot be overruled; in the case of disagreement, both opinions will be provided in any subsequent reports. The medical reviewer will assign expectedness.

The MRC CTU is undertaking the duties of the trial Sponsor and is responsible for the reporting of SUSARs and other SARs to the regulatory authorities and the research ethics committees, as appropriate. This responsibility is delegated to country PIs for relevant reporting requirements in individual countries.

The MRC CTU will also keep all investigators informed of any safety issues that arise during the course of the trial.

Pharmaceutical companies will also be notified of all reportable events according to the agreed contractual arrangements.

8 QUALITY ASSURANCE & CONTROL

8.1 RISK ASSESSMENT

The Quality Assurance (QA) and Quality Control (QC) considerations have been based on a formal Risk Assessment, which acknowledges the risks associated with the conduct of the trial and how to address them with QA and QC processes. QA includes all the planned and systematic actions established to ensure the trial is performed and data generated, documented and/or recorded and reported in compliance with the principles of GCP and applicable regulatory requirements. QC includes the operational techniques and activities done within the QA system to verify that the requirements for quality of the trial-related activities are fulfilled. This Risk Assessment has been reviewed by the CTU's Research Governance Committee (RGC) and has led to the development of a Data Management Plan (DMP), Safety Reporting Plan and Monitoring Plan which will be separately reviewed by the Quality Management Advisory Group (QMAG).

8.2 CENTRAL MONITORING AT CTU

Each site will be responsible for its own data entry and local trial management. Data will be entered into the online trial database directly at the site. The site will retain the original CRFs\worksheets. Data stored on the central database will be checked at CTU for missing or unusual values (range checks) and checked for consistency within children over time. If any problems relating to data quality are identified, the site will be contacted and asked to verify or correct the entry. Changes will be made on the original CRF\worksheet and entered into the database at the site. CTU will also send reminders for any overdue and/or missing data with the regular inconsistency reports of errors.

Other essential trial issues, events and outputs will be detailed in the Monitoring Plan that is based on the trial-specific Risk Assessment.

8.3 ON-SITE MONITORING

Staff from MRC CTU at UCL will visit clinical sites to validate and monitor data, and independent local monitors will be employed in each country to make regular visits to trial sites. The frequency, type and intensity for routine monitoring and the requirements for triggered monitoring will be detailed in the Monitoring Plan. This plan will also detail the procedures for review and sign-off.

A detailed site initiation visit with training will be performed at each study site by staff from the CTU. The site initiation visits will include training in the administration and side effects of study drugs, as well as the trial procedures.

Monitoring and site training will be carried out at least twice a year at each site by CTU staff or Africa-based monitors. The monitoring will adhere to the principles of GCP. The CRFs\worksheets of 5-10 children enrolled will be reviewed at the first monitoring visit. A sample of no less than 5 children will be selected by CTU for review at subsequent visits. Priority will be given to selecting children for whom the CRFs\worksheets have not been previously monitored.

Monitors will:

- verify completeness of the Investigator Site File
- confirm adherence to protocol

- review eligibility verification and consent procedures
- look for missed clinical event reporting
- verify completeness, consistency and accuracy of data being entered on CRFs\worksheets
- verify completeness, consistency and accuracy of PK study data and samples
- evaluate drug accountability
- provide additional training as needed

The monitors will require access to all patient medical records including, but not limited to, laboratory test results and prescriptions. The investigator (or delegated deputy) should work with the monitor to ensure that any problems detected are resolved.

8.3.1 DIRECT ACCESS TO CHILDREN'S RECORDS

Participating investigators should agree to allow trial-related monitoring, including audits, ethics committee review and regulatory inspections by providing direct access to source data and documents as required. Parental/caregiver consent must be obtained for this. Such information will be treated as strictly confidential and will in no circumstances be made publicly available.

The following data should all be verifiable from source documents:

- signed consent forms
- dates of visits including dates any trial specimens were taken and processed in the laboratory
- eligibility and baseline values for all children
- child clinical and laboratory data
- clinical endpoints
- serious adverse events, adverse events and notable events
- dates drug dispensed and (if necessary) drugs returned
- pharmacy/clinic drug logs
- concomitant medication dispensed

Not all such information will be monitored; rather the monitoring plan will describe a risk-based approach to monitoring based on ongoing random samples of patient clinical and laboratory data, which may be increased if issues are identified.

8.3.2 CONFIDENTIALITY

We plan to follow the principles of the EU General Data Protection Regulation 2016/679 and the UK Data Protection Act regardless of the countries where the trial is being conducted. In particular, the investigator must ensure that children's anonymity will be maintained and that their identities are protected from unauthorised parties. Children will be assigned a trial identification number and this will be used on CRFs\worksheets; children will not be identified by name. The investigator will keep securely a patient trial register showing Study IDs, name, initials and date of birth, held only at the local site. The unique Study ID (or laboratory tracking number) will identify all laboratory specimens, CRFs\worksheets, and other records and no names will be used on forms or samples, in order to maintain confidentiality. Copies of the child's immunisation records will be taken to provide an objective assessment of immunisations received (rather than relying on self-report), but names and any other personal identifiers (eg hospital number) will be blocked out before copies are taken. All records will be kept in locked locations. Clinical information will not be released without written permission, except as necessary for monitoring by the trial monitors.

9 STATISTICAL CONSIDERATIONS

9.1 METHOD OF RANDOMISATION

Randomisation will be stratified by site (5 sites, each recruiting 220 children). This factor has been chosen because of practicality (see below) and because it has the potential to modify treatment effects (i.e. lead to interaction) due to variation in other clinical management across sites, meaning forcing balance across the randomised groups is most important for this factor. Sites also vary in local standard of care of their most commonly used backbone IV antibiotics (allowed by the trial, see inclusion criteria in [Section 3](#)). All other factors should be balanced between groups by the randomisation. The other randomisation in the factorial design is also effectively a stratifier, and hence ensures balance for each randomisation with respect to the other – effectively each child is randomised to one of eleven groups (oral drug × duration (10 groups) plus continuous IV). If instead there were two separate randomisation lists for the oral drug and the total antibiotic duration, then by chance randomised groups for the former could be imbalanced with regard to the latter randomisation (and vice versa).

Randomisation lists will be prepared by staff at CTU under the direction of the Trial Statistician using random permuted blocks with variable size, stratified by clinical site. See [Section 4.1](#) for details of randomisation practicalities.

9.2 OUTCOME MEASURES

9.2.1 PRIMARY OUTCOME MEASURE

The primary outcome measure is:

- re-admission to hospital or death within 28 days post-randomisation (all-cause)

9.2.2 SECONDARY OUTCOME MEASURES

Efficacy/effectiveness secondary outcomes (assessed in all children) are:

- Proportion of children experiencing CAP-related readmission to hospital or CAP-related death within 28 days post-randomisation (CAP-relatedness adjudicated by the independent Endpoint Review Committee)
- Length of stay required during the index hospitalisation (days) (excluding any additional day remaining in hospital solely for the purpose of trial-related pharmacokinetic studies, see [Section 10.1](#)), and total days of stay in hospital up to 28 days
- Proportion of children dying within 28 days post-randomisation (all-cause mortality)
- Total days of supplemental oxygen during index hospitalisation
- Total days of antibiotic exposure during 28 days post-randomisation, including antibiotics received during the initial hospitalisation and antibiotics self-reported by parents/carers at follow-up visits
- Proportion of children requiring modification of randomised antibiotics for any reason other than early stopping, or requiring a subsequent course of antibiotics for any reason up to 28 days (also considered as separate components)
- Proportion of children requiring modification of randomised antibiotics for inadequate response, or additional courses in the index hospitalisation for CAP relapse

Safety secondary outcomes (assessed in all children) are the proportion of children:

- Experiencing SAEs, including hospital-acquired infections

- Experiencing grade 3 or 4 adverse events
- Experiencing antibiotic-related adverse events
- Experiencing key solicited events (reflecting common drug toxicities), specifically diarrhoea, vomiting and gastrointestinal disorders, skin rashes, thrush/candida
- Modifying antibiotics for antibiotic-related adverse events (i.e. toxicity)
- Experiencing specified clinical complications including sepsis, lung abscess, empyema
- Experiencing line complications (complications related to IV access)

Note that by definition a hospital-acquired infection prolongs hospitalisation so is an SAE following [Section 7](#). Therefore, the SAE secondary endpoint will include all hospital-acquired infections.

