Finally, there is no evidence for how long children with serious chest infections actually need to be on antibiotics. The longer people take antibiotics, the more likely it is that the other bacteria that we all live with us (and not the ones making us sick!) will become more resistant to antibiotics. This would mean that antibiotics won’t work as well for infections in the future.

So, we want to give children just enough antibiotics to make them well now, but not so many antibiotics that bacteria develop more resistance and the antibiotics perhaps won’t work next time.

Surprisingly almost no studies have looked at exactly how long children with serious chest infections need to take antibiotics to get better.

In this study, all children will start on the World Health Organisation (WHO)-recommended injectable antibiotics. When they are well enough to take drugs by mouth, they will be to move to one oral antibiotic called co-amoxiclav, or another oral antibiotic called amoxicillin, or they will stay on injectable antibiotics. This would be decided by chance (“randomisation”).

Both of these oral drugs should be highly effective, but we want to find out if co-amoxiclav is actually any better.

Co-amoxiclav is mostly given to children as a liquid, and needs to be kept cool. In the trial we will use tablets that become liquid when mixed with small amounts of other liquids (e.g. water) instead. If co-amoxiclav really is better, we need to make sure that these tablet formulations become more widely available.

We also don’t know how long the antibiotic treatment needs to last. Children will be randomised to get their antibiotics for 4, 5, 6, 7 or 8 days in total. These durations are used in different parts of the world and there is no evidence that any one is better than the other.

We will follow children for 28 days over the telephone and through face to face visits to find out whether they have had any problems. We will focus on whether they have to be admitted to

hospital again or whether they have died. We will also look at how long they have to stay in hospital (since parents/carers typically have to pay for this), how many antibiotics children take during the month after being admitted to hospital, how much they need other treatments like extra oxygen, and how much all their care costs.

[figure not shown]

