Secondary Outcome Measure(s)	
For the main trial (PediCAP-A), within 28 days of randomisation:
 
 ▪ CAP-related readmission or CAP-related mortality ▪ Length of stay required during the index hospitalisation, and overall through 28 days ▪ Mortality (all-cause) ▪ Duration of supplemental oxygen during the index hospitalisation ▪ Total days of antibiotic exposure through 28 days ▪ Modification of randomised antibiotics for any reason except early stopping or receipt of subsequent course of antibiotics for any reason ▪ Modification of randomised antibiotics for inadequate response or additional courses for CAP relapse ▪ Serious adverse events ▪ Grade 3 or 4 adverse events ▪ Adverse events of any grade related to antibiotics ▪ Key solicited events, specifically diarrhoea, vomiting and gastrointestinal disorders, skin rash, thrush/candida ▪ Modification of antibiotics for adverse reactions ▪ Specific clinical complications, including sepsis, lung abscess, empyema ▪ Line complications ▪ Antimicrobial resistance (see Substudies below) ▪ Cost and cost-effectiveness (see Substudies below)
Randomisation	
In the main trial (PediCAP-A), children will be allocated 1:1 to the different step-down options (amoxicillin or co-amoxiclav in 7:1 ratio) and 1:1:1:1:1 to the different total duration of antibiotic therapy using a factorial design, or to continue on intravenous antibiotics (11 groups in total)
 
In the Phase II PK trial (PediCAP-B), children will be allocated 1:1 to co-amoxiclav in either 4:1 or 14:1 ratios

Number of Participants to be Studied	
1100 in the main trial (PediCAP-A) (100 per randomised group)
 
120 in the Phase II PK trial (PediCAP-B) (60 per formulation)

SUMMARY INFORMATION TYPE	SUMMARY DETAILS
Duration	Each child will be followed for 28 days from randomisation. The trial will recruit over 23 months (total 2 year duration)

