1.4.4 SERVICE EVALUATION IN RECRUITING SITES

To inform protocol development, a short service evaluation was conducted in four of the five trial sites (South Africa, Uganda, Zambia and Zimbabwe) in February 2018. Brief details of consecutive children aged 2 months to 10 years admitted for antibiotic treatment of pneumonia were recorded for 2 weeks or 30 children, whichever was achieved first. In total, 93 children were recorded across the sites (12-32 children/site). Of these, 79 (85%, 40/79 males) children were commenced on intravenous antibiotics at admission to hospital. The commonest intravenous regimens were those recommended by the WHO and included in the eligibility criteria below (56/79 – 71% -

benzylpenicillin or ampicillin plus aminoglycoside; 12/79 – 15% - ceftriaxone or equivalent third generation cephalosporin). The modal duration of hospitalisation was 4 days, and 47/79 (59%) children were hospitalised for 4 days or longer. Only 6/79 (8%) children were discharged from hospital without further oral antibiotic treatment, and half of these had been treated in hospital for 7 days or longer already. Further relevant results for the 79 children treated with intravenous antibiotics are summarised in **Table 3** below.

Table 3: Additional details of 79 children treated with intravenous antibiotics in trial sites

VARIABLE	SUMMARY			
Age (in months)	Median	IQR	Min	Max
	12	6-18	3	98
Weight (in kg)	Median	IQR	Min	Max
	7.8	6.6-9.3	2.9	22.2
	Children weighing <4kg n=3			
Underlying disease/risk factor	Malnutrition	HIV exposure	Chronic neurological disease	HIV infection
	13/79 (16%)	7/79 (9%)	6/79 (8%)	3/79 (4%)
Investigations	Chest X-ray obtained		Inflammatory marker measured	
	31/79 (39%)		63/79 (81%)	
Supportive therapies during stay	Supplemental Oxygen	IV fluids	Nasogastric feeds/fluids	
	51/79 (65%)	14/79 (18%)	5/79 (6%)	

Note: IQR=interquartile range.

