The main criteria for moving from intravenous to oral antibiotics is that the child should have improved clinically, be currently clinically stable or continuing to improve, and be well enough to take medication by mouth, i.e. can ingest and keep down the dispersible tablets when made up in a small amount of liquid, and hence oral absorption of the antibiotic is likely to be good. Children may move to oral medication whilst inpatients (e.g. if they are still receiving supplemental oxygen). See MOP for further details.

Children should be discharged on oral medication as soon as they are clinically stable and have received and retained at least one dose of oral antibiotics. See MOP for further details.

Table 7: Dosing for oral amoxicillin and co-amoxiclav

FORMULATION	WEIGHT BAND	# TABLETS AM	# TABLETS PM	# TABLETS DAILY	DAILY DOSE (MG)
Amoxicillin (250mg tablets)	3 - <6kg	1	1	2	500
	6 - <10kg	2	1	3	750
	10 - <14kg	2	2	4	1000
	14 - <20kg	3	3	6	1500
	20 - <25kg	4	4	8	2100
	25 - <35kg	5	5	10	2500
Co-amoxiclav 7:1 (200/28.5mg tablets)	3 - <6kg	1	1	2	400/57
	6 - <10kg	2	2	4	800/114
	10 - <14kg	3	2	5	1000/142.5
	14 - <20kg	4	4	8	1600/228
	20 - <25kg	5	5	10	2000/285
	25 - <35kg	6	6	12	2400/342
Co-amoxiclav 4:1 (250/62.5mg)	3 - <6kg	1	1	2	500/125
	6 - <10kg	2	1	3	750/187.5
	10 - <14kg	2	2	4	1000/250
	14 - <20kg	3	3	6	1500/375
	20 - <25kg	4	4	8	2000/500
	25 - <35kg	5	5	10	2500/625
Co-amoxiclav 14:1 (150/10.725mg)	3 - <6kg	2	1	3	450/32.175
	6 - <10kg	3	2	5	750/53.625
	10 - <14kg	4	3	7	1050/75.075
	14 - <20kg	5	5	10	1500/107.25
	20 - <25kg	7	6	13	1950/139.425
	25 - <35kg	8	8	16	2400/171.6

Note: inclusion criteria include weights up to 30kg ([Section 3](#)), but dosing table includes weights up to 35kg to allow for dehydrated children gaining weight during admission, and to align with WHO HIV weight-bands.

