5.4 INADEQUATE RESPONSE TO TREATMENT

The management of potential inadequate response to intravenous antibiotics or the randomised antibiotic regimen and/or relapse after the completion of therapy as prescribed will be based on a

range of potential scenarios. These will be fully described in the MOP, but example scenarios are included in **Table 8** below.

Table 8: Example scenarios of inadequate response or relapse

TIMING	SCENARIO	ACTION*
DURING PRIMARY HOSPITAL ADMISSION OR WITHIN ORIGINALLY RANDOMISED TREATMENT COURSE		
Any time	Child clinically deteriorates, e.g. with severe respiratory distress or septic shock	Chest X-ray is strongly recommended. Treat with injectable antibiotics as per normal standards of care (e.g. moving to second line treatment regimen according to local standard of care).
	Positive blood culture or other test result suggesting more serious manifestation of severe CAP	Manage according to local standard of care (e.g. moving to different intravenous antibiotics, treating for longer than original randomisation depending on clinical status of the child).
After two days IV	No improvement in clinical status on IV therapy	Manage according to local standard of care (e.g. moving to cloxacillin if staphylococcal pneumonia is suspected, or to second-line, or repeating laboratory tests where available). Consider TB.
After oral switch	Child has persistent symptoms and signs of a respiratory tract infection after oral switch, e.g. with continued fever, tachypnoea, tachycardia, but remains clinically stable. Appears to be tolerating oral medication.	Continue oral medication as randomised: most likely infection is viral. Also consider evaluation for TB.
	Child has persistent symptoms and signs of a respiratory tract infection and is NOT tolerating oral medication due to severe persistent vomiting or diarrhoea	Switch to IV or injectable antibiotics as per normal standards of care.
AFTER DISCHARGE FROM PRIMARY ADMISSION OR AFTER COMPLETION OF INITIAL RANDOMISED COURSE		
Any time	Child has persistent symptoms of a mild respiratory tract infection, with no signs of pneumonia	No treatment for CAP. A child with persistent cough and fever for more than 2 weeks and signs of pneumonia after adequate antibiotic treatment should be evaluated for TB.
	Child has signs of pneumonia, and fulfils the diagnostic criteria of non-severe CAP	Treat as per normal standards of care. Consider TB.

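### The secondary outcome on inadequate response or CAP relapse has two definitions, and the Section 9.2.2 wording leaves out relapse courses given after discharge

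*Protocol*

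**What the plan says.** The outcome appears twice in the Protocol.

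- **Summary of Trial, Secondary Outcome Measure(s).** The list opens with "For the main trial (PediCAP-A), within 28 days of randomisation" and includes "Modification of randomised antibiotics for inadequate response or additional courses for CAP relapse". It has a 28-day window and no restriction on where the child is.
- **Section 9.2.2.** The outcome is "Proportion of children requiring modification of randomised antibiotics for inadequate response, or additional courses in the index hospitalisation for CAP relapse". The relapse part is now tied to the first hospital stay, and no 28-day window is attached.

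The bullet directly above it in Section 9.2.2 covers modification, or a later course for any reason, and does run to 28 days. The narrower window is therefore specific to this one outcome. The amendment log in Section 18 records no change to it, so both wordings are current.

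Three other parts of the Protocol bear on the point:

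- On discharge, Section 5.3.1 says "Children should be discharged on oral medication as soon as they are clinically stable", provided that one oral dose has been given and retained. Section 5.2.1 keeps children in the intravenous group in hospital for their whole 5-day course.
- Table 8 in Section 5.4 has a block for events after discharge or after completing the course. One scenario is "Child has signs of pneumonia, and fulfils the diagnostic criteria of non-severe CAP", for which the listed action does not mention admission.
- Section 6.6 says that post-discharge antibiotic prescriptions are asked about at every scheduled contact.

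**The concern.** A pre-specified efficacy outcome with two definitions leaves a choice open in an open-label trial. Here the two versions can give different answers.

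The trial compares lengths of treatment. The allocated durations are identical until the shortest course ends on day 4, so any relapse caused by stopping sooner can only arise from then on. By that time many step-down children could be at home. A relapse component counted only during the index stay would be insensitive to what the duration randomisation is meant to test. Section 1.4.2 plans duration-response curves for secondary as well as primary outcomes, and missing post-discharge relapses would tend to flatten this one.

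The observation window also depends on allocation. The intravenous group stays in hospital for 5 days by design, whereas an important aim of oral step-down is to shorten the stay. The two are not watched for equal time under an in-hospital definition.

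**Working it through.** The Protocol gives no design figure for this outcome, so there is none to reproduce. The check compares the two texts, with one piece of arithmetic.

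**1. The definitions side by side**

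| Element | Summary of Trial | Section 9.2.2 |
|---|---|---|
| Modification for inadequate response | counted, to 28 days | counted, no index-stay limit |
| Additional course for CAP relapse, index stay | counted | counted |
| Additional course for CAP relapse, after discharge | counted, to 28 days | not counted |

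The conflict lies wholly in the last row.

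**2. When a post-course relapse can be seen in hospital**

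Let D be the allocated duration and L the length of the index stay, both in days and treated as starting together. A relapse after the course has ended can fall in the index stay only if L > D. The Lay Summary gives the durations: "Children will be randomised to get their antibiotics for 4, 5, 6, 7 or 8 days in total". The smallest D is 4, so a child with L < 4 cannot contribute such an event in any duration group.

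**3. How many children that might be**

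Section 1.4.4 reports: "The modal duration of hospitalisation was 4 days, and 47/79 (59%) children were hospitalised for 4 days or longer".

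- Stayed 4 days or longer: 47/79 = 59.5% (the Protocol gives 59%).
- Stayed less than 4 days: 79 − 47 = 32, and 32/79 = 40.5%, about 41%.

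If trial stays were like these, about 41% would have left before even the 4-day course ended. For D = 5 to 8, the share leaving before the course ends is at least as large.

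**4. Effect on the duration comparison**

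Let q be the share of relapse courses that start after discharge, and suppose that it is the same in each duration group. Then, for the relapse component,

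observed difference = (1 − q) × true difference.

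The Protocol gives neither q nor a relapse rate. The attenuation could lie anywhere from none (q = 0) to complete (q = 1). The 41% describes lengths of stay and is not an estimate of q.

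**5. Effect on oral versus intravenous**

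The intravenous group is in hospital for at least its 5-day course. Oral groups may leave earlier. A longer window can only add counted events, so the unequal window would tend to raise the intravenous count relative to the oral count.

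**6. Where a post-discharge relapse course is counted under Section 9.2.2**

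| Relapse after discharge | This outcome | Any-reason later course, 28 days | CAP-related readmission or death | Primary outcome |
|---|---|---|---|---|
| Leads to readmission or death | no | yes, if a course is given | yes, if adjudicated CAP-related | yes |
| New course without readmission, child survives | no | yes | no | no |

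The second row is the gap: the event is counted, but in no outcome specific to CAP.

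**The case against.** The best defence is that the restriction may be deliberate. Courses in the index stay are recorded by study staff together with reasons for change, whereas post-discharge courses rest on parents' reports. The Endpoint Review Committee adjudicates deaths and readmissions, not outpatient prescriptions. Section 9.2.4 prefers objective outcomes because the trial is open-label. Attributing an outpatient course to CAP relapse is softer evidence. This stands as a reason to report the two components separately. It does not explain why the Summary gives the 28-day version, and Section 9.2.2 states no such rationale.

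The second defence is that little is lost. Half of the composite is unrestricted: a child who fails at home while still on the course and is switched is counted. The any-reason outcome takes in every later course to 28 days, and relapses that lead to readmission or death enter the primary outcome. This also stands, and it limits the consequence.

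A reader might infer more than the Protocol supports:

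- **That both effects favour short courses.** They do not. The unequal window between intravenous and oral groups would tend to favour oral step-down. Across the five durations, discharge depends on stability and one retained oral dose, not on allocated duration, so the Protocol sets no difference in window by duration. What remains there is attenuation.
- **That this is the main efficacy outcome after the primary.** The Protocol does not rank its secondary outcomes; this is the last of seven efficacy bullets.
- **That at least 41% of relapses would be missed.** The survey covered routine care in children aged 2 months to 10 years admitted for pneumonia. The trial requires severe pneumonia and excludes low CRP, so trial stays could be longer or shorter.

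**Conclusion.** The two definitions conflict in the current text and should be reconciled. Under the Section 9.2.2 wording, the relapse component omits courses started after discharge, where relapse after a 4 to 8 day course could mostly occur. That short courses do cause such relapses is the question under test, not an established fact.

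The likely consequences are attenuated differences between durations on this outcome and a longer counting window for the intravenous group. Their size cannot be computed, because no relapse rate or timing is given. The only figure available is 32/79 (41%) leaving hospital before day 4, and it rests on the assumption that trial stays resemble the service evaluation.

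The damage is confined to one component of one secondary outcome. The uncovered event is a post-discharge CAP relapse treated without readmission. The primary outcome, sample size and power do not change. This is a should-fix.

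**What to change.** 1. In Section 9.2.2, remove the restriction of relapse courses to the index hospitalisation and state the window as 28 days from randomisation, so that it matches the Summary of Trial. Carry the same wording into the analysis plan.
2. Confirm that the CRF records why each post-discharge antibiotic course was given. Section 6.6 names only the type and duration of additional treatment. The telephone contact in Section 6.1.4.A asks about acute illnesses and prescriptions but does not say that the indication is recorded.
3. Report index-stay and post-discharge relapse courses separately as well as combined, so that a reader can see how far the result depends on parent-reported, unadjudicated courses.

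**Cost.** One line of text and a check of the CRF. If the indication is already captured, no new data are needed; if not, one item is added to contacts that already take place. The downside is the softer attribution of outpatient courses in an open-label trial, which the separate reporting makes visible.
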